6.4 Safety

The safety analysis will be performed in the population of patients valid for the long-term safety analysis set. All tabulations will be descriptive only. Data from LTE phase until end of study will be shown. Absolute values and changes from Week 52 (which is the baseline for the LTE phase analysis) will be shown.

Adverse events starting in the main phase and continuing into the LTE phase will be included.

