The SAP for the main treatment phase of the study was finalized prior to unblinding to describe the evaluation the efficacy and safety of 52-week treatment (plus 30-day safety follow-up, when applicable) with riociguat compared to the placebo ([16277 Statistical Analysis Plan - Final Version 4_0](#)). The SAP describing the interim benefit-risk evaluation for the long term extension (LTE) phase was finalized on 12 JUL 2018 ([16277 Statistical Analysis Plan for Benefit-risk update version 1.0](#)). This SAP describes the complete evaluation of the LTE phase. Results from the final LTE analyses will be presented in the Addendum to the Clinical Study Report (CSR).

2. Study Objectives

The overall objective of the main phase of study 16277 was to evaluate the efficacy and safety of 52 weeks of treatment with riociguat versus placebo in subjects with dcSSc. For details on the primary and secondary objectives of the study, see the SAP of the main treatment phase.

The main focus of the evaluation of the LTE phase described in this SAP was to allow a continued exploratory assessment of benefit risk profile of riociguat.

3. Study Design

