4.5.1 Definition of baseline and handling of repeated measurements

Baseline for the main phase is defined as the last set of non-missing measurements taken prior to the first intake of study medication, called ‘baseline for main treatment phase’.

In case of multiple measurements per post baseline visit, the last non-missing value per visit will be taken for analysis.

For LTE phase, Week 52 will serve as baseline measurement for LTE (‘baseline for LTE phase’) to be compared with measurements during the LTE phase.

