5.1 Assignment of analysis sets

Long term safety analysis set will be used in LTE phase. It will consist of all patients randomized and treated with study medication (FAS), who have continued treatment with study medication in the LTE phase of the study.

6. Statistical Methodology

Although dose titration is in use, the descriptive analyses will be shown to the following treatment groups:

- Patients randomized to riociguat in the main phase who stayed on riociguat in the LTE phase (called Riociguat-Riociguat in outputs)
- Patients randomized to placebo in the main phase who switched to riociguat in the LTE phase (called Placebo-Riociguat in outputs)
- Total of all patients.

Any comparison between the two treatment groups defined above should be done very carefully, since all patients received riociguat in the LTE phase (ie. initial randomization is not preserved). The decision whether or not a patient takes part in the LTE phase may depend on the treatment which was given in the main phase and thus the groups may not be comparable. All results are purely exploratory.

Number of decimal places for summary statistics will be the following:

Figure 6–1 - Decimal places for summary statistics

Statistic	Number of digits
Minimum, maximum	Same as original data
Mean, median	1 more than in original data
SD	2 more than in original data
Frequencies (%)	1 decimal place

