6.2 Efficacy

In the LTE phase, the following endpoints will be described:

- mRSS
- Pulmonary function testing:
 - FVC% predicted
 - FVC (l)
 - DLco% predicted
 - DLco (mmol/min/kPa)
- PROs / HRQoL:
 - Scleroderma Health Assessment Questionnaire (SHAQ)
 - Short Form 36 (SF-36)
 - Patient-Reported Outcomes Measurement Information System (PROMIS)-29
 - University of California, Los Angeles, Scleroderma Clinical Trial Consortium Gastrointestinal Scale (UCLA SCTC GIT) 2.0.
- Worsening of end-organ disease (cardiac, renal, pulmonary, gastrointestinal & digital ischemia)
- Digital ulcer net burden
- Proportion of patients developing new digital ulcers
- Evaluate digital ulcers for patients with and without DUs at baseline by line plots
- All cause mortality
- Composite endpoint will be assessed from Week 52 to the end of the study (in addition, each individual endpoint will be described separately):
 - mRSS progression (defined as an increase in mRSS by > 4 units or >=20%)
 - worsening of FVC (defined as an absolute change of FVC% predicted \leq -10)

- new organ involvement (as defined in CRISS Step 1 main SAP).

Main study phase and LTE phase data will be shown in summary tables. Change from baseline and change from Week 52 (which is the baseline for the LTE analysis) will be shown. Progression/regression/improvement/worsening rates will be assessed from Week 52 until the end of the study.

6.2.1 mRSS

- Summary statistics for mRSS
- mRSS progression rate (defined as increase in mRSS by > 5 units and $\geq 25\%$)
- mRSS regression rate (defined as decrease in mRSS by > 5 units and $\geq 25\%$)
- mRSS progression rate (defined as increase in mRSS by > 4 units or $\geq 20\%$)
- Percentage of subjects with $\geq 20\%$, 40% , or 60% improvement in mRSS
- Percentage of subjects with $\geq 20\%$, 40% , or 60% worsening in mRSS

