6.4.2 Laboratory data

The safety evaluation of laboratory data will include:

- Incidence rates of treatment-emergent laboratory values outside of normal range.
- Incidence rates of pre-specified laboratory data abnormalities.
- Descriptive analysis of continuous laboratory parameters, and their changes from baseline (i.e. Week 52) by visit.
- Categorical analysis of transitions from low, normal, high from baseline (i.e. Week 52) to post baseline.

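### Extension changes in laboratory values, vital signs and weight are measured from Week 52 only, which is an on-riociguat value for Riociguat-Riociguat patients, and the Total column mixes on-drug and pre-drug baselines

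*SAP*

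**What the plan says.** SAP section 4.5.1 defines two baselines. For the main phase: "Baseline for the main phase is defined as the last set of non-missing measurements taken prior to the first intake of study medication". For the extension: "For LTE phase, Week 52 will serve as baseline measurement for LTE", with no distinction by original arm. It also takes the last non-missing value when a post-baseline visit has several measurements.

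Safety uses only the second baseline. SAP 6.4 says: "Absolute values and changes from Week 52 (which is the baseline for the LTE phase analysis) will be shown", and limits the safety display to data from the extension phase onward. SAP 6.4.2 plans "Descriptive analysis of continuous laboratory parameters, and their changes from baseline (i.e. Week 52) by visit" and "Categorical analysis of transitions from low, normal, high from baseline (i.e. Week 52) to post baseline". SAP 6.4.3 takes changes in weight, vital signs and pulse oximetry from Week 52 as well.

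Efficacy is handled differently. SAP 6.2 shows main-phase and extension data together and says: "Change from baseline and change from Week 52 (which is the baseline for the LTE analysis) will be shown".

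SAP section 6 sets the display columns. One group is "Patients randomized to riociguat in the main phase who stayed on riociguat in the LTE phase", the second is patients who switched from placebo, and the third is a Total of all patients. The stated focus of the extension analysis (SAP section 2) is "to allow a continued exploratory assessment of benefit risk profile of riociguat".

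**The concern.** Week 52 means different things in the two groups. For Placebo-Riociguat it is the visit at which riociguat starts. For Riociguat-Riociguat it follows titration and maintenance on the drug, and only sham titration comes after it. A blood pressure or haemoglobin that had fallen on riociguat by Week 52 and stayed down would give a mean change near zero, and in the laboratory transition table a low-to-low entry. The Total column averages these two contrasts under one label.

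At stake is the use of the tables for the benefit-risk aim. The group with the longest exposure is not set against its own pre-riociguat values in any of these extension outputs. A reader who takes the Total change as the effect of starting riociguat would read it too low.

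**Working it through.** The plan gives no figure on this point to reproduce. The check sets out exposure at baseline, then the arithmetic of the columns, then the visit schedule.

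**Inputs**
- Main phase: 10 weeks of titration plus 42 of maintenance (protocol synopsis).
- Start of riociguat at Visit 12 for placebo patients; sham titration for the others (SAP 3.1 and 3.1.1).
- Allocation 1:1, about 65 per arm (protocol 4.1). The number per group entering the extension is not given.
- Visit 12 procedures: protocol 7.1.2.5 and Table 7-2. Laboratory schedule: protocol 7.6.2.

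**1. Exposure at the Week 52 baseline**
- Riociguat-Riociguat: 10 + 42 = 52 weeks.
- Placebo-Riociguat: 0 weeks before that visit's dose.

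**2. What the change columns show**

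Let d be a persistent shift caused by starting riociguat, f the fraction of it that emerges only after Week 52 in Riociguat-Riociguat, and w the Placebo-Riociguat share of the extension set. Here d, f and w are all assumptions.
- Riociguat-Riociguat change from Week 52 = f·d
- Placebo-Riociguat change from Week 52 = d
- Total = w·d + (1 − w)·f·d

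With f = 0, Total is 0.4d at w = 0.4, 0.5d at w = 0.5 and 0.6d at w = 0.6.

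With w = 0.5, Total = 0.5d + 0.5·f·d, that is 0.55d at f = 0.10, 0.625d at f = 0.25 and 0.75d at f = 0.50.

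Measured from the main-phase baseline, Riociguat-Riociguat would show d.

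**3. Laboratory transitions (illustration)**

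Assume that starting riociguat moves 10% of patients from normal to abnormal and that 65 + 65 enter. The true count is 0.10 × 130 = 13. From Week 52 only the Placebo-Riociguat transitions appear as new: 0.10 × 65 = 6.5, or 6.5/130 = 5% of Total. The others are counted as already abnormal.

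**4. Which Visit 12 reading is the baseline**

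At Visit 12 blood pressure and heart rate are measured before the dose, again about 2 hours after it, and again before the 3 to 4 hour blood sample. SAP 4.5.1 does not say that the Week 52 baseline is the pre-dose value, and its rule for repeated measurements picks the last one. Applied to Visit 12, that rule could make the Placebo-Riociguat vital-sign baseline a reading taken after the first riociguat dose.

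**5. Can a pooled column be rescued by time since first riociguat dose?**

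Over the first year of exposure, routine laboratory times for Riociguat-Riociguat are weeks 10, 26, 39 and 52. Placebo-Riociguat patients are sampled at study weeks 62, 64, 76, 88 and 100; subtracting 52 gives weeks 10, 12, 24, 36 and 48. Only week 10 coincides, so re-alignment does not give a usable Total without further visit-window rules.

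**The case against.** The strongest reply is that first-year effects belong to a better analysis. Protocol 8.4.3 plans laboratory and vital-sign changes from baseline by treatment group and visit in the randomised phase, and the SAP introduction assigns that phase to a separate plan. Change from Week 52 then answers a legitimate question: what happens with further exposure. The Placebo-Riociguat column keeps its own before-and-after contrast, no test or decision depends on the Total, and SAP section 6 calls all results exploratory and urges care in comparing the groups.

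Much of this stands. A reader might infer that the extension cannot show any effect of riociguat in the longer-exposed group, or that safety information is lost. The documents do not support that. Changes emerging after Week 52 would appear, though without a control. Absolute values, abnormal laboratory incidences and vital-sign category counts by visit are shown. Treatment-emergent adverse events are dated from first study drug, and main-phase events still ongoing at extension entry are summarised. FVC and DLco have both baselines under efficacy.

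The reply does not remove the gap. The main-phase report stops at Week 52 and is not restricted to patients who continued, so its mean changes cannot simply be added to the extension changes, and two separate shift tables do not give patient-level transitions. Absolute values under SAP 6.4 cover the extension only, so the pre-riociguat level is not beside them. The SAP's caution is about comparing groups and says nothing about the Week 52 baseline or the Total.

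**Conclusion.** The point holds for a limited set of outputs: change tables for laboratory values, vital signs and weight, and the laboratory transition table. In these, a shift that arose in Riociguat-Riociguat by Week 52 and persists shows as no change. The Total change shows the Placebo-Riociguat share of such a shift: half with equal groups, 40% to 60% for shares of 40% to 60%, and more if part of the effect comes after Week 52. These proportions follow from the definitions. The group shares, and the existence and size of any shift, are assumptions; nothing in the documents shows that a given parameter is affected. The open choice of Visit 12 reading is a further ambiguity, for vital signs only.

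It is worth correcting because the remedy is cheap and serves the stated benefit-risk aim. It does not undermine the adverse event analysis or the main-phase results.

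**What to change.** - In SAP 6.4.2 and 6.4.3, add by-group change from the main-phase baseline for laboratory values, vital signs and weight, matching SAP 6.2, and add laboratory low/normal/high transitions from that baseline.
- In SAP 4.5.1, state that the Week 52 baseline is the pre-dose Visit 12 value.
- Show change from Week 52 by group without a Total, or footnote that the Total mixes on-drug and pre-drug baselines.
- Do not add a pooled Total re-aligned by time since first riociguat dose, because the visit schedules do not match.
- Leave pulse oximetry as it is: protocol 7.6.18 first schedules it at Visit 9, so it has no planned pre-treatment value.

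The cost is extra table shells and programming. No new data are needed: the baseline is already defined, and protocol Table 7-1 schedules all three kinds of measurement at screening and Visit 1. The added tables will be uncontrolled and restricted to patients who went on into the extension. In Riociguat-Riociguat these are patients who stayed on riociguat through the first year, which can understate harm. Concomitant medication is also largely free in the extension. The tables should be read descriptively.

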7.1.2.2 Visit 1 – Main treatment phase - Baseline (Day 0, Week 0)

The following assessments will be performed at Visit 1 (Day 0 of study drug treatment):

Before intake of study medication

- Reconfirmation of eligibility (assessment of inclusion/exclusion criteria; Section 5.1)
- Questionnaires (see Section 7.6.13)
- Update of medical and surgical history, if needed (see Section 7.2.2)
- Smoking history
- Physical examination, including weight
- Vital signs (blood pressure and heart rate). Blood pressure and heart rate will be measured at all visits with the patient in a sitting position, after the patient has been at rest for at least 5 minutes. The same arm is always used for these measurements (see Section 7.6.5).
- Patient and physician assessments of Raynaud's attacks, and patient to return completed 7-day diary (see Section 7.6.12)
- Digital ulcer net burden assessment (see Section 7.6.10)
- Patient's and physician's global assessment (see Section 7.6.15)
- Patient interference with skin assessment (see Section 7.6.16)

- Assessment for the presence or absence of tendon friction rubs (see Section 7.6.17)
- Blood samples for safety (see Section 7.6.2)
- Blood sample for biomarkers to be obtained before the start of study drug treatment (see Section 7.6.3)
- Pregnancy test (urine) for all women of childbearing potential (see Section 7.6.1)
- 12-lead ECG for centralized reading. A standard 12-lead ECG will be obtained with the patient in the supine position after resting for at least 5 minutes (See Section 7.6.7)
- Skin biopsy to be obtained before the start of study drug treatment (see Section 7.6.9)
- Recording and assessment of AEs (see Section 7.5.1)
- Concomitant therapy
- Randomization (IxRS) to study drug treatment with either riociguat or placebo (see Section 6)
- Dispensation of study drug and first intake by patient

After intake of study medication

- Blood sample for PK (see Section 7.4)
 - PK blood sample between 1 – 2 hours after administration of the morning dose of study medication
 - PK blood sample between 3 – 4 hours after administration of the morning dose of study medication
- Vital signs (blood pressure and heart rate) should be measured within 20 minutes prior to each post-dose PK sampling with the patient in a sitting position and after the patient has been at rest for at least 5 minutes. The same arm is always used for these measurements (see Section 7.6.5).

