4.5.2 Definition of treatment-emergence

Values will be considered treatment-emergent if they start within 2 calendar days after the last day of study drug administration, i.e. the treatment-emergent window will be 2 days.

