6.1.3 Study medication duration and exposure

Study medication duration and exposure will be summarized by treatment group and overall.

The duration of study medication (in days) is derived by calculating the study medication durations by the following formula: period (last dose date – first dose date + 1). Descriptive statistics of treatment duration as well as frequency counts by treatment duration categories will be presented. Dose titration by visit, dose titration sequence and reasons for up- and down-titration by visit and dose will also be summarized using frequency counts from titration phase of LTE period.

The formula for compliance is:

$$\frac{(\text{Total dispensed} - \text{total returned})}{(\text{Days between visits} \times \text{dose}[\# \text{ of pills}])} \times 100$$

= What was taken / What should've been taken

x 100 = % Compliance

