6.4.1 Adverse events and mortality

The incidence of AEs (includes incidence of TEAEs and incidence of post-treatment AEs) will be summarized using MedDRA (version 21.1) preferred terms grouped by primary system organ class. The version number of MedDRA relevant for study evaluation will be stored in the study database.

The incidence of treatment-emergent AEs (TEAEs) occurring during the LTE phase will be tabulated by treatment groups defined for LTE phase. More specifically, AEs are considered to be treatment-emergent if they have started or worsened after first application of study drug up to 2 days after end of treatment with study drug.

An overall summary of the number and percentage of patients with TEAEs will be presented by treatment groups for events from Week 52 to the end of the study. This summary will include the number and the percentage of patients with drug-related TEAEs, treatment emergent serious adverse events (TESAEs), drug-related TESAEs, maximum intensity, AEs leading to permanent discontinuation and AEs with outcome of death.

Incidences of subjects with TEAEs occurring during LTE phase will be summarized by treatment arm and MedDRA terms using frequency tables for the following AE types:

- TEAEs
- Drug-related TEAEs
- TESAEs
- Drug-related TESAEs
- TEAEs of special interests
- Drug-related TEAEs of special interest

Tables for maximum intensity of TEAEs, TESAEs and drug-related TEAEs will be provided.

TEAEs which occurred during the main phase and were ongoing (i.e. not reported as “recovered/resolved” or “recovered/resolved with sequelae”) at the entry in LTE phase will be summarized.

Incidences of TEAEs and TESAEs per 100 person-years will be tabulated. The rate per 100 person-years is calculated as

$$\text{Rate per 100 person-years} = \text{number of events} / (\text{total drug exposure in years} / 100),$$

where 365.25 days are taken as one year.

The incidence of all post-treatment AEs (i.e., AEs occurring more than 2 days after end of treatment with study drug) will be tabulated separately.

AEs with outcome of death will be tabulated from Week 52 to the end of the study.

SAEs, deaths, AE leading to discontinuation and AEs of special interest (as defined in the [protocol Section 7.5.1.6](#)) will be listed. The date, relative day (to study medication) will be included.

Further summaries of AEs by intensity and outcome, may be provided, consistent with Bayer Global Medical Standards.

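### The extension SAP does not re-anchor treatment-emergence to the first extension dose, so events that began on placebo can be counted as TEAEs under Placebo-Riociguat

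*SAP*

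**What the plan says.** The SAP reports the extension in two groups and a total. One group is defined in SAP Section 6 as "Patients randomized to placebo in the main phase who switched to riociguat in the LTE phase".

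Four statements govern which adverse events are shown for that group:

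- SAP 6.4, in the opening text that precedes all the AE tables: "Adverse events starting in the main phase and continuing into the LTE phase will be included".
- SAP 6.4.1, the definition: "AEs are considered to be treatment-emergent if they have started or worsened after first application of study drug up to 2 days after end" (meaning the end of dosing).
- SAP 6.4.1, the scope: the TEAE tables cover TEAEs that occur in the extension, and the overall summary covers events from Week 52 to the end of the study.
- SAP 6.4.1, a further summary: "TEAEs which occurred during the main phase and were ongoing" when the patient entered the extension.

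SAP 4.5.2 adds only the end of the window: "Values will be considered treatment-emergent if they start within 2 calendar days after the last day of study drug administration".

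SAP 6.4.1 also plans TEAE and TESAE rates per 100 person-years, calculated as the number of events divided by total drug exposure in years over 100. Exposure is described in SAP 6.1.3: "The duration of study medication (in days) is derived by calculating the study medication durations by the following formula: period", that is, last dose date minus first dose date plus 1.

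**The concern.** For a patient in the Placebo-Riociguat group, riociguat starts at Visit 12. Suppose dizziness begins at Week 20 on placebo and is unchanged at Week 52. It falls after the first dose of study drug, so it meets the 6.4.1 definition, and because it continues into the extension, 6.4 says it is included. Nothing states that it stays out of the extension TEAE tables, and it also qualifies for the ongoing-at-entry summary.

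This matters because SAP Section 2 gives the focus of the extension analysis as a continued exploratory look at riociguat's benefit-risk profile, and the ex-placebo patients are the only ones who start riociguat within it. Their column is where a reader will look for new-onset tolerability. The overview of Protocol Amendment 6 records that the DMC had noted more palpitations and dizziness in patients with interstitial lung disease. The TEAE tables by that condition in SAP 6.4.4 use the same definition.

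The person-year rate has the same gap in both its terms.

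**Working it through.** **Where the clock starts.**

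1. Placebo counts as study drug. Protocol 7.1.2.2 lists "Randomization (IxRS) to study drug treatment with either riociguat or placebo" at Day 0, followed by dispensing and first intake.
2. SAP 4.5.1 ties the first intake of study medication to the main-phase baseline. It resets the baseline for measurements to Week 52, but says nothing about the AE window.
3. The 6.4.1 definition is essentially that of Protocol 8.4.3, carried over without an extension-specific start. Read literally, the clock starts at Week 0 for both groups.
4. The partial-date rule in SAP 4.3 refers only to the start of study medication, so it does not place an event before or after the switch.

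**What the scope limits settle.** They favour onset in the extension, but *occurring* is not defined as onset, and the unreset definition follows immediately as a clarification of that very sentence. The ongoing-at-entry summary is not said to be the only place for main-phase events, and it applies the label TEAE to events from the placebo period.

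**The rate.** SAP 6.1.3 limits its titration summaries to the extension's titration phase but puts no such limit on duration. In 6.4.1 the rate sentence names no phase for the events, and the formula names none for the exposure.

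**Direction of bias.** The documents contain no figure to reproduce: no AE counts, no number of patients entering the extension, no extension exposure. The following is an illustration only, and all three inputs are assumptions. Let T = 1 to 2 years on riociguat in the extension, λ = 2 to 4 new events per patient-year, and c = 0.5 to 2 placebo-onset events ongoing per patient at Week 52. The placebo period is 364/365.25 = 0.997 years, taken as 1.

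- Extension onsets over extension exposure: 100λ = 200 to 400 per 100 person-years.
- Carry-over in the numerator only: 100(λT + c)/T, a ratio of 1 + c/(λT) to the first line. The smallest is 1 + 0.5/(4×2) = 1.06 (425 against 400). The largest is 1 + 2/(2×1) = 2.0 (400 against 200).
- Placebo year in the denominator only: ratio T/(T + 1), which is 1/2 = 0.50 at T = 1 and 2/3 = 0.67 at T = 2.
- Both: 100(λT + c)/(T + 1), from (2×1 + 0.5)/2 × 100 = 125 to (4×2 + 2)/3 × 100 = 333. The ratio is (T + c/λ)/(T + 1), which falls below 1 when c < λ and rises above 1 when c > λ. Over these inputs it runs from (1 + 0.5/4)/2 = 0.56 to 1.00.

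The same data can therefore give a rate that is too high or too low, depending on how two unstated limits are programmed.

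**The case against.** The best defence is that SAP 6.4.1, read as a whole, already confines the tables to the extension. SAP 6.4 says that data from the extension onward will be shown. The definition sentence follows directly on the extension limit and can be read inside it. When 6.4.1 speaks of main-phase TEAEs it uses *occurred* for the phase of onset, so by the same usage extension TEAEs are those with onset in the extension. The inclusion sentence in 6.4 is then carried out by the ongoing-at-entry summary and nothing else. In addition, SAP 4.5 places the treatment-emergence flags in analysis datasets specified in a separate document that is not available here. Section 6 calls all results purely exploratory, the safety tabulations are descriptive only, and SAP 3.1 records that development in this indication was stopped.

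Much of this stands. The narrow reading is reasonable and may be what was intended, and no test or decision threshold depends on these tables. But the reader has to infer it against a literal definition and an unqualified inclusion sentence. The dataset specification might settle the matter, but the SAP should not need it to decide which events count. The caution in Section 6 concerns the comparability of the two groups; it does not warn that a riociguat column may hold placebo-onset events. The defence is weakest for the rate, where no extension limit is attached to either term.

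**Conclusion.** The point holds as a conflict within the SAP. The treatment-emergent definition and the inclusion sentence admit placebo-onset events to the Placebo-Riociguat column, while the scope limits and the separate summary point to their exclusion. The person-year rate is unrestricted in both terms and could be biased either way.

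A reader might infer more, and the documents do not support it:

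- That placebo-onset events *will* be reported as extension TEAEs. This is one reading of conflicting text, not a stated rule.
- That exposure *is* counted from Week 0. The SAP gives no start date; a Week 0 start is possible but not stated.
- That carry-over could not be detected afterwards. The ongoing-at-entry summary would show much of it, and SAEs, deaths, AEs leading to discontinuation and AEs of special interest are listed with dates and relative days.

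No size can be derived from the documents. The factors above (1.06 to 2.0 for carry-over alone, 0.50 to 0.67 for the placebo year in the denominator alone) rest entirely on assumed inputs and show direction, not expected magnitude. The correction should be made because it removes a route to misattributed events in the only group that starts riociguat in the extension. The descriptive, exploratory purpose limits the consequence.

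**What to change.** 1. In SAP 6.4.1, for all extension tables, define TEAEs as events that start or worsen on or after the first dose assigned at Visit 12 and no later than 2 days after the last dose.
2. In SAP 6.4, replace the inclusion sentence with a statement that main-phase events continuing unchanged appear only in the ongoing-at-entry summary already planned.
3. In the rate formula and SAP 6.1.3, limit both events and exposure to the extension, counting exposure from the Visit 12 dose.

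Apply all three to both groups, so that the two columns cover the same window.

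The cost is SAP wording and one derivation flag, with no new data collection. Worsening has to be identified from the AE records as collected: the items listed in Protocol 7.5.1.3 include date of appearance, duration and severity but no separate date of worsening, so the SAP should say how worsening is recognised.
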